9.4 Response Criteria

9.4.1 Evaluation of Target Lesions

Complete Response (CR): Disappearance of all target lesions. Any pathological lymph nodes (whether target or non-target) must have reduction in short axis to <10 mm.

Partial Response (PR): At least a 30% decrease in the sum of the diameters of target lesions, taking as reference the baseline sum diameters.

Progressive Disease (PD): At least a 20% increase in the sum of the diameters of target lesions, taking as reference the smallest sum on study (this includes the baseline sum if that is the smallest on study). In addition to the relative increase of 20%, the sum must also demonstrate an absolute increase of at least 5 mm. (Note: the appearance of one or more new lesions is also considered progressions).

Stable Disease (SD): Neither sufficient shrinkage to qualify for PR nor sufficient increase to qualify for PD, taking as reference the smallest sum diameters while on study.

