5.3 Microwave Ablation

Microwave ablation will be predominantly used on metastatic soft tissue lesions and will include use of Covidien's Evident™ MWA System. Microwave ablation is performed under ultrasound, CT, and occasional fluoroscopic guidance with CT fluoroscopy available for intermittent use in probe placement and CT monitoring of ablation. Procedures will be performed on an outpatient basis, but patients can be admitted for observation post-procedure as deemed appropriate by the treating interventional radiologist. Patients are generally under moderate conscious sedation with midazolam and fentanyl with continuous nurse monitoring of pulse oximetry, blood pressure, cardiac rhythm and rate, and respirations. General endotracheal anesthesia is allowed in cases felt clinically appropriate as deemed by the interventional radiologist. One percent lidocaine alone or a 1:1 mixture of 1% lidocaine and 0.25% bupivacaine or 0.5% ropivacaine is used for local and periosteal anesthesia.

Microwave antennae from Covidien (Mansfield, MA) are either introduced into the lesion co-axially through a bone biopsy needle or directly into the lesions that are amenable to such, i.e., soft tissue, lung, liver, and large lytic lesions with extensive bone destruction. For blastic lesions, a hand drill may be needed for bone access. For larger lesions, additional antennae are placed in parallel arrangement approximately 1.0 cm apart. Antenna positioning and adequate coverage of the tumor is confirmed with CT imaging. When necessary, thermal protection and bowel protection with balloon interposition or with carbon dioxide dissection or hydrodissection will be used.

Ablations will be performed according to the manufacturer's recommendations in the package insert. After completion of ablation, tract ablation is performed as the probe is withdrawn.

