7.0 STUDY CALENDAR

Baseline evaluations are to be conducted within 3 weeks prior to start of protocol therapy. Scans and x-rays must be done no more than 3 weeks prior to the start of ablation.

	Baseline	Ablation	1 day after ablation	1 month after ablation	Follow-up ^d	Progression
Physical exam, incl. medical history, weight, VS, PS	X					
CBC	X					
CMP	X					
PT/PTT and INR	X					
Pregnancy test ^a	X					
IR evaluation ^b	X					
CT or PET scan					X ^d	
FACT-G7	X		X	X		X
BPI short form	X		X	X		X
Adverse events		X ^c				
Survival follow-up						X ^e

a: Women of childbearing potential only

b: Patients must have 10 or fewer treatable lesions when enrolled in the study and will be seen in consultation by an experienced interventional oncologic radiologist with evaluation of available PET, CT, MR, and US images for eligibility and lesion accessibility

c: Tracked for 30 days following ablation

d: The patients will be imaged as per routine care at the following time points: 6 weeks post first-procedure, every 9 weeks for the first year, every 12 weeks for the second year, and every 6 months for 5 years or until death or radiographic progression, whichever comes first.

e. After progression, patients will be followed every 3 months for survival only.

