9.0 MEASUREMENT OF EFFECT

9.1 Antitumor Effect – Solid Tumors

There will be another PET/CT at 42 +/- 3 days following the last procedure (approximately 6 weeks post-procedure) and one every 9 weeks thereafter until progression of disease. All imaging is standard of care.

For the purposes of this study, patients should be re-evaluated for response every 9 weeks. In addition to a baseline scan, confirmatory scans should also be obtained 4 weeks (not less than 4) weeks following initial documentation of objective response.

Response and progression will be evaluated in this study using the new international criteria proposed by the revised Response Evaluation Criteria in Solid Tumors (RECIST) guideline (version 1.1) [Eur J Ca 45:228-247, 2009]. Changes in the largest diameter (unidimensional measurement) of the tumor lesions and the shortest diameter in the case of malignant lymph nodes are used in the RECIST criteria.

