11.0 STATISTICAL CONSIDERATIONS

11.1 Power

Our power analysis is based on the following hypotheses. The null hypothesis assumes that the 3-month progression-free survival (PFS) for treatment with ablation therapy is

overall 20% for patients with metastatic sarcoma. We hypothesize in the alternative hypothesis that the 3-month PFS will be at least 40% with ablation therapy. This is based on data from a clinical trials database used to provide reference values for conducting phase II studies in sarcoma with PFR as the principal endpoint (5). An enrollment of 36 patients can achieve at least 80% power to conclude that the alternative hypothesis is true based on a two-sided test of one-sample proportion at a significance level of 0.05.

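### Progression for the primary endpoint is defined in two unreconciled ways, and the RECIST rules can misclassify an ablated lesion in either direction

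*Combined protocol and SAP*

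**What the plan says.** **PFR definition.** Sections 2.1 and 9.4.5 define PFR progression as recurrence at an ablated lesion or a new lesion. Neither mentions a sum of diameters, and neither gives an imaging criterion or a reference scan for recurrence.

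**RECIST rules.** Section 9.1 says that response and progression are evaluated by RECIST 1.1, with no exemption for PFR. Section 9.4.1 sets target-lesion progression at a rise of at least 20% and at least 5 mm, "taking as reference the smallest sum on study (this includes the baseline sum if that is the smallest on study". Section 9.4.2 requires non-target progression to reflect a change in overall disease status rather than growth of one lesion.

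**Baseline.** Baseline imaging precedes treatment. Section 7.0: "Scans and x-rays must be done no more than 3 weeks prior to the start of ablation". Section 9.3 allows up to 4 weeks.

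**Coverage.** Ablation is meant to cover the tumour. Section 5.3: "Antenna positioning and adequate coverage of the tumor is confirmed with CT imaging". No zone size or margin is given.

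**First post-ablation scan.** Section 9.1: "There will be another PET/CT at 42 +/- 3 days following the last procedure", then every 9 weeks. Note d of section 7.0 counts the 6 weeks from the first procedure instead. Neither section makes this scan a new reference.

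**The concern.** RECIST diameters assume that what is measured is tumour. Here the target lesions are deliberately replaced by ablation zones, and a zone that covers the tumour with a margin is wider than the tumour was. No section says how to measure a zone or excludes treatment-related enlargement from progression. A reader who follows section 9.4.1 can therefore record progression where sections 2.1 and 9.4.5 see none. Conversely, recurrence at one margin is an event under sections 2.1 and 9.4.5 but may not move the target sum enough, or may be discounted under section 9.4.2.

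The sole primary endpoint is at stake. False failures lower the observed PFR and cost power. Missed recurrences raise it and inflate the type I error. A false failure is also hard to undo, because note d of section 7.0 ends imaging at radiographic progression.

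**Working it through.** **1. The plan's own figure.** Section 11.1 gives a null of "overall 20% for patients with metastatic sarcoma", an alternative of 40%, and a "two-sided test of one-sample proportion at a significance level of 0.05". By the normal approximation,

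n = [z(0.975)·√(p0(1−p0)) + z(0.80)·√(p1(1−p1))]² / (p1−p0)² = (1.9600×0.4000 + 0.8416×0.4899)² / 0.20² = 1.1963² / 0.04 = 35.78.

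This rounds up to 36, with power 0.802. The stated N is reproduced and is not in dispute.

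**2. Which scan decides.** On section 9.1's timing, scans fall about 6 and 6 + 9 = 15 weeks after the last procedure. Three months is about 13 weeks, so only the first scan precedes the landmark. At that scan the smallest sum on study before it is the pre-ablation sum.

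**3. False progression at the first scan.** Assume a net margin m on each side, the whole zone measured, and no involution. For one lesion of diameter D the rise is 2m, or 2m/D in relative terms. Both conditions are met when 2m ≥ 5 mm and D ≤ 10m.

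| Assumed m (mm) | Rise 2m (mm) | Lesions meeting the rule |
|---|---|---|
| 2 | 4 | none (below 5 mm) |
| 2.5 | 5 | D ≤ 25 mm |
| 3 | 6 | D ≤ 30 mm |
| 5 | 10 | D ≤ 50 mm |
| 7 | 14 | D ≤ 70 mm |

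Example: a 20 mm lesion with a 5 mm margin reads 30 mm, a rise of 50%. Section 3.1 admits lung and liver lesions from 10 mm, up to 50 mm when multiple and 70 mm when single. The 5 mm floor applies to the sum, so it protects a single target more than several: two 20 mm lesions with a 2 mm margin rise by 8 mm on 40 mm, exactly 20%.

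**4. Missed local recurrence.** Section 9.2 allows five targets, at most two per organ. With five 30 mm targets the sum is 150 mm and 20% of it is 30 mm. If the others are unchanged, one recurring lesion must grow 30 mm. With one 30 mm target, 6 mm suffices. Ablated lesions beyond the fifth are non-target, where section 9.4.2 discounts growth of a single lesion.

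**5. Masking by zone shrinkage.** Take a baseline of 30 mm and a week-6 zone of 35 mm (+17%, stable). Suppose the zone alone would then shrink to 25 mm while a marginal nodule grows. The threshold stays at 1.2 × 30 = 36 mm, so growth just under 36 − 25 = 11 mm is hidden. If the 25 mm value is recorded first, it becomes the reference and 5 mm of regrowth is progression. Masking is thus confined to growth that coincides with shrinkage between scans, which on section 9.1's timing falls mainly after 3 months.

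**6. What misclassification would do to the test.** The shares are assumed.

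| True non-progressors scored as progressed | Observed PFR when truth is 40% | Power (normal approximation) |
|---|---|---|
| 0% | 40% | 80% |
| 5% | 38% | 73% |
| 10% | 36% | 64% |
| 20% | 32% | 45% |
| 30% | 28% | 25% |

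In the other direction, if 5% or 10% of true progressors are missed under the null, the observed rate is 0.20 + 0.05×0.80 = 24% or 0.20 + 0.10×0.80 = 28%. With success at 13 or more of 36, the exact upper-tail error rises from 0.018 to 0.070 or 0.183.

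**The case against.** The strongest reply is that sections 2.1 and 9.4.5 already define the endpoint. If they govern, zone enlargement is not an event, a marginal recurrence is one, and neither error follows. This stands as far as it goes: a reader might infer that the plan scores the primary endpoint by the target sum, and the documents do not establish that. But section 9.1 applies RECIST to progression without exception, the only numeric rule is in section 9.4.1, and the PFR definition gives readers nothing to apply to a scan. The conflict remains.

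Three further points limit the size:

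- Margins, involution and the measuring habit are all assumed. A radiologist may not record the whole zone as tumour.
- Bone lesions are non-measurable under section 9.2 and so lie outside the sum rule.
- Section 9.4.2 lets the treating physician's opinion prevail in exceptional non-target cases, so its single-lesion clause is not an absolute bar.

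All three stand. They narrow the exposure but do not say which definition decides.

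**Conclusion.** The point holds as a definitional conflict that reaches the primary endpoint. At the only scan before 3 months on section 9.1's timing, a single measurable lesion up to 30 mm (3 mm margin) or 50 mm (5 mm margin) can meet the written progression rule through treatment effect alone, and none can at 2 mm. This rests on assumed margins, no involution and measurement of the whole zone. In the other direction, summing over targets and the single-lesion clause can leave a true local recurrence unscored. The documents give no misclassification rate, so the effects on power and type I error are illustrations only.

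Stronger readings are not supported:

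- A reader might infer that the reference is always the pre-ablation sum. It is the smallest sum on study, so it moves down once a lower sum is recorded.
- A reader might infer that shrinking zones hide recurrences at the 3-month landmark. The falling reference limits this, and it acts mainly later.
- A reader might infer that every eligible lesion is exposed at a 5 mm margin. Single lung or liver lesions above 50 mm and bone lesions are not.
- A reader might infer that the bias could never be signed. At the first scan the zone-size error runs towards false progression, which is conservative against the 20% null. Section 8.0 collects tumour measurements on the imaging schedule, so a re-read is plausible.

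**What to change.** In sections 9.4.1, 9.4.2 and 9.4.5, state that:

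1. The definition in sections 2.1 and 9.4.5 governs PFR.
2. For PFR, ablated lesions are excluded from the 20% sum rule and from the single-lesion clause of section 9.4.2.
3. Each ablated lesion is assessed individually. Viable or new tumour at or next to the ablation site is local recurrence at any scan, including the first. Enlargement of the zone alone is judged only against the smallest post-ablation measurement of that lesion.
4. A named scan determines 3-month status. The 6-week anchor must be reconciled between section 7.0 (first procedure) and section 9.1 (last procedure).

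Making the 6-week scan a new baseline for the sum would not be enough. In the example of working step 5 the threshold would rise from 36 mm to 1.2 × 35 = 42 mm, and hidden growth from just under 11 mm to just under 17 mm.

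**Cost.** The change uses scans already planned and leaves N = 36 as it is. It is more than tidying: readers must judge residual or recurrent tumour explicitly at the first scan, and counting residual tumour there settles a matter that section 9.4.5 leaves open. Zone enlargement alone cannot be scored until a second post-ablation scan, about week 15 on section 9.1's timing, so 3-month status would rest on visible tumour at the ablation sites and on new lesions.

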9.4.2 Evaluation of Non-Target Lesions

Complete Response (CR): Disappearance of all non-target lesions and normalization of tumor marker level. All lymph nodes must be non-pathological in size (<10 mm short axis).

Note: If tumor markers are initially above the upper normal limit, they must normalize for a patient to be considered in complete clinical response.

Non-CR/Non-PD: Persistence of one or more non-target lesion(s) and/or maintenance of tumor marker level above the normal limits.

Progressive Disease (PD): Appearance of one or more new lesions and/or unequivocal progression of existing non-target lesions. Unequivocal progression should not normally trump target lesion status. It must be representative of overall disease status change, not a single lesion increase.

Although a clear progression of “non-target” lesions only is exceptional, the opinion of the treating physician should prevail in such circumstances, and the progression status should be confirmed at a later time by the review panel (or Principal Investigator).

9.4.3 Evaluation of Best Overall Response

The best overall response is the best response recorded from the start of the treatment until disease progression/recurrence (taking as reference for progressive disease the smallest measurements recorded since the treatment started). The patient's best response assignment will depend on the achievement of both measurement and confirmation criteria.

For Patients with Measurable Disease (i.e., Target Disease)

Target Lesions	Non-Target Lesions	New Lesions	Overall Response	Best Overall Response when Confirmation is Required*
CR	CR	No	CR	>4 wks. Confirmation**
CR	Non-CR/Non-PD	No	PR	>4 wks. Confirmation**
CR	Not evaluated	No	PR	
PR	Non-CR/Non-PD/not evaluated	No	PR	
SD	Non-CR/Non-PD/not evaluated	No	SD	Documented at least once >4 wks. from baseline**
PD	Any	Yes or No	PD	no prior SD, PR or CR
Any	PD***	Yes or No	PD	
Any	Any	Yes	PD	

* See RECIST 1.1 manuscript for further details on what is evidence of a new lesion. ** Only for non-randomized trials with response as primary endpoint. *** In exceptional circumstances, unequivocal progression in non-target lesions may be accepted as disease progression. Note: Patients with a global deterioration of health status requiring discontinuation of treatment without objective evidence of disease progression at that time should be reported as “symptomatic deterioration.” Every effort should be made to document the objective progression even after discontinuation of treatment.
				

For Patients with Non-Measurable Disease (i.e., Non-Target Disease)

Non-Target Lesions	New Lesions	Overall Response
CR	No	CR
Non-CR/non-PD	No	Non-CR/non-PD*
Not all evaluated	No	not evaluated
Unequivocal PD	Yes or No	PD
Any	Yes	PD
* 'Non-CR/non-PD' is preferred over 'stable disease' for non-target disease since SD is increasingly used as an endpoint for assessment of efficacy in some trials so to assign this category when no lesions can be measured is not advised		

9.4.4 Duration of Response

Duration of overall response: The duration of overall response is measured from the time measurement criteria are met for CR or PR (whichever is first recorded) until the first date that recurrent or progressive disease is objectively documented (taking as reference for progressive disease the smallest measurements recorded since the treatment started).

The duration of overall CR is measured from the time measurement criteria are first met for CR until the first date that progressive disease is objectively documented.

Duration of stable disease: Stable disease is measured from the start of the treatment until the criteria for progression are met, taking as reference the smallest measurements recorded since the treatment started, including the baseline measurements.

9.4.5 Other Definitions

Progression-free rate: PFR is defined as the percentage of patients with no progression (local recurrence of an ablated lesion or the appearance of a new lesion) at 3 months after ablation.

Overall survival: OS is defined as the time from diagnosis of metastatic disease to the time of death.

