2.0 OBJECTIVES

2.1 Primary Objectives

To determine the progression-free rate at 3 months in patients with metastatic sarcoma stable on chemotherapy whose lesions have undergone ablation. PFR is defined as the percentage of patients with no progression (local recurrence of an ablated lesion or the appearance of a new lesion) at 3 months after ablation.

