3.0 PATIENT SELECTION

3.1 Inclusion Criteria

1. Histologically or cytologically confirmed high-grade metastatic sarcoma that has been stable on 6-12 cycles of one chemotherapeutic regimen (cytotoxic or biologic) although a change in chemotherapy is allowed if it is a result of toxicity/tolerability rather than progression. A patient must not have evidence of progression at any time while on chemotherapy in order to be eligible for this trial.
2. Measurable disease defined as lesions that can be accurately measured in at least one dimension (longest diameter to be recorded) as ≥ 10 mm with CT scan, PET CT, or MRI exam.
3. At least 18 years of age.
4. ECOG performance status ≤ 2 (Karnofsky $\geq 60\%$, see Appendix A)
5. Normal bone marrow and organ function as defined below:
 - a. Leukocytes $\geq 3,000/\text{mcl}$
 - b. Absolute neutrophil count $\geq 1,500/\text{mcl}$
 - c. Platelets $\geq 100,000/\text{mcl}$
 - d. Total bilirubin $\leq 1.5 \times \text{IULN}$ or $3 \times \text{IULN}$ with normal ALT and AST in patients with Gilbert's disease
 - e. $\text{AST(SGOT)/ALT(SGPT)} \leq 3.0 \times \text{IULN}$

- f. Creatinine less than the institutional upper limit of normal
OR
Creatinine clearance ≥ 50 mL/min/1.73 m²
 - g. INR < 1.5 or patient off Coumadin at the time of ablation
6. No more than 10 treatable lesions as evaluated by an experienced interventional oncologic radiologist for eligibility and lesion accessibility as the ablation of more than 10 lesions becomes technically infeasible. These lesions must be treated in a two- to three-week time period from initial interventional radiology evaluation. Lung and liver lesions can range from 1 cm to 7 cm for a single lesion and no greater than 5 cm for multiple lesions. There are no size criteria for the osseous lesions.
 7. The lesions will be amenable to a safe, ultrasound/computed tomographic/fluoroscopic guided percutaneous approach. The targeted metastases must be sufficiently separateable from the central nervous system, major peripheral motor nerves, bowel, and bladder. All lesions must be amenable to treatment.
 8. If patients have received radiation therapy, there must be a one-month washout period.

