5.4 Criteria for Ablation

Ablation will be postponed for ANC<1500 or platelets <100,000. Ablation will also be postponed if the creatinine or bilirubin are elevated above baseline until those lab values normalize.

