5.6 Evaluability

All patients who undergo ablation are evaluable for toxicity. Patients are evaluated from date of first procedure and for 30 days thereafter.

All patients who undergo ablation are evaluable for disease response provided they have had at least one disease assessment.

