5.9 Duration of Therapy

Tumor ablation is a one-time procedure. If at any time prior to or during ablation, the constraints of this protocol are considered to be detrimental to the patient's health and/or the patient no longer wishes to proceed with ablation, this treatment should be discontinued and the reason(s) for discontinuation documented in the case report forms.

Because the ablation procedures are intended to replace maintenance chemotherapy, chemotherapy should not resume following ablation therapy. If the treating physician feels it is warranted (i.e., the patient develops a lesion that is not amenable to ablation), then the patient will be considered to have progressed and will be taken off trial and replaced.

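### The primary progression definition omits growth of a known lesion left unablated, RECIST 1.1 partly includes it, and the plan does not say which governs the endpoint

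*Combined protocol and SAP*

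**What the plan says.** The combined protocol and SAP carries two accounts of progression.

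- **The endpoint definition.** Section 9.4.5 defines the PFR thus: "percentage of patients with no progression (local recurrence of an ablated lesion or the appearance of a new lesion) at 3 months after ablation". Section 2.1 gives the same two events: "no progression (local recurrence of an ablated lesion or the appearance of a new lesion".
- **The general rule.** Section 9.1 states: "Response and progression will be evaluated in this study using the new international criteria", meaning RECIST 1.1. Under 9.4.1, progressive disease includes "At least a 20% increase in the sum of the diameters of target lesions", with an absolute rise of at least 5 mm. Section 9.4.2 adds unequivocal progression of existing non-target lesions. Neither test asks whether the lesion was ablated.

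Section 11.1 calls the endpoint 3-month PFS and gives no definition of progression, so it does not settle which account applies.

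On completeness of treatment, 3.1 admits up to 10 lesions, all of which must be treatable, and adds: "These lesions must be treated in a two- to three-week time period from initial interventional radiology evaluation". Section 5.5 foresees more than one procedure. Section 5.9 provides that if, before or during ablation, the protocol is judged harmful to the patient or "the patient no longer wishes to proceed with ablation, this treatment should be discontinued". Section 5.4 lists laboratory reasons for delay, among them: "Ablation will also be postponed if the creatinine or bilirubin are elevated above baseline until those lab values normalize". Section 5.6 sets the analysis set: "All patients who undergo ablation are evaluable for disease response provided they have had at least one disease assessment". It does not require that every lesion was treated.

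**The concern.** A two-event definition is sufficient when every known lesion has been ablated, because disease can then reappear only at a treated site or somewhere new. It leaves a gap when a known lesion remains untreated, and the protocol's own rules make that possible.

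In a patient with such a lesion, failure of the strategy may show itself as growth of exactly that lesion, off chemotherapy. Under the two-event wording this patient has no event and enters the numerator as a success. The misclassification runs one way, in favour of ablation, and it affects the endpoint on which the trial is judged.

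**Working it through.** **1. The plan's own figure.** Inputs from 11.1: null 20%, alternative 40%, two-sided 0.05, power 80%, one-sample proportion.

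n = [(1.960 × √(0.2 × 0.8) + 0.842 × √(0.4 × 0.6)) / 0.2]² = [(0.784 + 0.412) / 0.2]² = 35.78, rounded up to 36. Power at 36 is 80.2%. The sample size is reproduced and does not depend on this point.

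**2. One patient under both rules.** Take six known lesions, three ablated and three not. The untreated ones grow, nothing recurs at the ablated sites, and no new lesion appears.

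- Sections 2.1 and 9.4.5: neither listed event has occurred, so the patient is progression-free.
- Sections 9.1 and 9.4.1 to 9.4.3: progressive disease if the target sum rises by at least 20% and 5 mm, or if non-target growth is unequivocal.

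The same scans can give opposite primary outcomes.

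**3. How much RECIST would catch.**

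- Section 9.2 limits targets to five in all and two per organ, against up to 10 treatable lesions, so an untreated lesion may be non-target.
- Take five equal targets of diameter d, four ablated and unchanged. The sum is 5d and a 20% rise is 0.20 × 5d = d. The one untreated lesion must go from d to 2d, that is, double.
- Section 9.2 classes bone lesions as non-measurable, although 3.1 admits them without a size limit. Section 9.4.2 says non-target progression should reflect a change in overall disease and not an increase in one lesion. It leaves exceptional cases to the treating physician, with later confirmation.

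So RECIST closes the gap only in part.

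**4. Size.** Each misscored patient moves the PFR by 1/36 = 2.8 percentage points. The documents give no rate of incomplete ablation, so I assume k = 0 to 3 true progressors are scored as progression-free. With a true rate of 20%, the expected number of progressors is 0.8 × 36 = 28.8, so 1 to 3 is about 3% to 10% of them. With X binomial (36, 0.20), the chance of an observed count of at least r is P(X ≥ r − k):

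| k | Shift in PFR (points) | Reach 12/36 | Reach 13/36 |
|---|---|---|---|
| 0 | 0 | 0.042 | 0.018 |
| 1 | 2.8 | 0.089 | 0.042 |
| 2 | 5.6 | 0.168 | 0.089 |
| 3 | 8.3 | 0.284 | 0.168 |

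Both cut-offs are shown because 11.1 does not say whether the test is approximate or exact. With standard error √(0.16/36) = 0.0667, 11/36 gives z = 1.58 and 12/36 gives z = 2.00, so the normal approximation rejects from 12. The exact upper tail at 12 is 0.042, above 0.025, so an exact test with 0.025 in each tail rejects from 13.

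**The case against.** The best defence is that 9.1 applies RECIST 1.1 to progression in this study without exception, so the parenthesis in 2.1 and 9.4.5 may be only a gloss on what progression usually looks like after complete ablation. On that reading, growth that meets the thresholds is progression. This stands as a possible reading. But 9.4.5 is the endpoint-specific definition, comes after the RECIST criteria, and has its own event list. Nothing ranks one above the other.

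Second, incomplete ablation departs from the design: entry requires every lesion to be treatable, and the schema has all ablation finished within 3 weeks. This also stands, and it limits the number of patients affected. But treatability at entry does not guarantee completion, and 5.6 keeps the incompletely treated patient. The delay rule in 5.4 is the weaker route. The study calendar schedules laboratory tests only at baseline, and nothing shows lesions being abandoned because of delay.

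Third, 5.9 treats a patient as progressed when the treating physician finds that chemotherapy must resume. That catches some of these patients. It depends on a treatment decision, though, and the same sentence has the patient replaced, so it does not define the endpoint.

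Fourth, regrowth at an ablated site that was never cleared would ordinarily be called local recurrence. I agree that this is mainly a question of wording.

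**Conclusion.** The point holds as an unresolved conflict between two definitions, with a gap that opens under one of them. If the PFR wording governs, growth of a known unablated lesion is not an event, and the error can only raise the PFR, by 2.8 points per such patient. If RECIST governs, part of that growth is still missed. If all lesions are ablated in every patient, the effect is zero.

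Three stronger readings are tempting and not supported:

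- A reader might infer that such patients definitely will be scored as successes, or can never be counted as failures. Section 9.1 prevents that conclusion.
- A reader might take 1 to 3 patients as an expected number. It is an assumption. Each must have incomplete ablation and growth in an untreated lesion by 3 months, with no new lesion and no local recurrence.
- A reader might conclude that the step from 11/36 to 12/36 decides the trial. That holds only under the normal approximation.

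The correction is worth making because it is cheap and the possible bias has one direction. The sample size is unaffected.

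**What to change.** In 2.1 and 9.4.5, define progression for the PFR as any of:

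- recurrent, or residual and growing, tumour at an ablated site;
- a new lesion;
- progression of any known baseline lesion that was not ablated.

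Judge the third item lesion by lesion with the protocol's existing thresholds: at least 20% and 5 mm over that lesion's smallest measurement, or unequivocal progression if it is non-measurable. Judging per lesion prevents stable ablated lesions from diluting the change and avoids an undefined notion of growth.

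State that this definition governs the primary endpoint, in place of the general rule in 9.1 where they differ, and that it applies to patients whose ablation was incomplete. Use the Ablation Form to identify which baseline lesions were treated, if it does not already; its content is not shown, and the covariate in 11.2 for total diameter of ablated lesions already needs much of this information.

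The cost is a short change in two sections, possibly one form field, and measurement of unablated measurable lesions outside the target set, which 9.2 does not now require. The observed PFR may be slightly less favourable.
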